## 8.10 Missing Data

For efficacy evaluation appropriate methods will be used to handle any missing data. The details of techniques for handling of missing data will be included in the SAP for the study which will be finalized prior to database lock.

# 8.11 Analysis Methods

A Statistical Analysis Plan (SAP) will be developed and approved before the database is locked. The SAP will present the detailed statistical methodology to be used in analyzing the efficacy and safety data from this trial. All inferential statistical analysis will be based on a two-sided test with a Type I error rate of 0.05.

All the efficacy analyses presented here will be conducted using the ITT, populations. All safety analyses will be conducted using the Safety population. Study data summaries will include the following:

## 8.11.1 Subject Disposition

The disposition of all subjects screened will be provided.	
	•

## 8.11.2 Demographic and Baseline Characteristics

Demographics and baseline characteristics will be summarized by treatment group using appropriate descriptive statistics.

## 8.11.3 Concomitant Medications/Therapies

## 8.11.4 Efficacy Analyses

## 8.11.4.1 Primary Analysis

The primary analysis will be conducted on the Intent-to-treat (ITT) population.

#### Primary Endpoint:

will be used to compare the proportion of subjects achieved a total LODS score  $\leq$  5 at or prior to 60 minutes post-randomization.

#### Secondary Endpoints:

• Proportion of subjects who achieved a LODS total score  $\leq 5$  at planned timepoints.

All secondary endpoints data will be presented and summarized according to the variable type:

- Continuous data summaries will include:
  - Number of observations, mean, standard deviation, median, and minimum and maximum values.

- Categorical data summaries will include:
  - Frequency counts and percentages.
  - 0
- Time-to-event data summaries will be using
  - Kaplan-Meier (K-M) methods to depict the data and Cox proportional hazards model for inferential statistics.

#### 8.11.5 Supportive Analysis

## 8.12 Safety Analyses

The Safety population will be used for the analysis of safety endpoints.

For continuous variables data will be summarized by treatment using n, mean, SD, minimum and maximum values. For categorical variables data will be summarized by treatment using frequency and percentage.

#### 8.12.1 Adverse Events

Adverse events will be coded using the most recent version of Medical Dictionary for Regulatory Activities (MedDRA). Treatment Emergent AE's (TEAE) are defined as events with an onset on or after the first randomized treatment. TEAEs will be summarized by treatment group, System Organ Class, and preferred term. The following TEAE summaries will be provided:

- Overall (i.e., regardless of severity or relationship to treatment)
- By severity grade (mild, moderate, severe, or life threatening for SAEs)
- By relationship to clinical trial treatment according to the mapping scheme below:
  - Potentially related: will include all adverse events with a relationship rating of "definitely", "probably" or "possibly".
  - Unlikely/not related: will include all adverse events with a relationship rating of "unlikely" or "unrelated".

In addition, separate summaries of serious adverse events, and adverse events resulting in discontinuation of study treatment will be presented.

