Study EGL-4104-C-1702 is a phase 2, multiple-site, open-label, randomized, 2-group parallel study of Ryanodex[®] for the treatment of PDIT, administered intravenously (IV) as adjuvant treatment to the current SOC, which is defined as body cooling and supportive measures, including treating related symptoms and any existing comorbidities. Due to the acute and serious nature of PDIT, more commonly occurring in young individuals attending mass gathering events (e.g. large music festivals and concerts), and the importance of early diagnosis and fast implementation of treatment, the study will be conducted at qualified pre-hospital emergency care facilities [PHEC]. The PHECs are medical units fully equipped and staffed to provide adequate emergency medical care to patients with PDIT. This study is designed to evaluate the safety and efficacy of Ryanodex[®] in this acutely ill patient population in an emergency setting, where study subjects are anticipated to be treated over a short period of time and then transferred to another medical facility or released, depending on their overall medical status. In order to standardize subject's evaluation, data collection and subsequent analysis, functioning of each organ system will be assessed individually and will also be conducted using the Logistic Organ Dysfunction System (LODS).

After diagnosis of PDIT, the Investigator should initiate SOC treatment as quickly as possible, and will assess the subject's eligibility for study participation. The Investigator will document subject's baseline status.

Body cooling measures should be stopped at the first instance of rectal temperature hypothermia.

Enrolled study subjects are expected to remain at the study site for a maximum of 6 hours after screening, prior to discharge from the study site. Subjects who require hospitalization beyond for the study after Screening (e.g., because of complications, adverse events [AEs], or other reasons) will complete the required study discharge procedures prior to their continuation of care outside of the study. The Investigator will make all reasonable efforts to obtain subjects' medical data from these medical facilities.

Logistic Organ Dysfunction System

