The Logistic Organ Dysfunction System (LODS) provides an objective tool for assessing organ dysfunction in critical patients. The LODS identifies organ dysfunction for 6 organ systems: neurologic, cardiovascular, renal, pulmonary, hematologic and hepatic, taking into account both the relative severity among organ systems and the level of severity within an organ system.

Standard of Care

Implementation of standard of care (SOC) should be initiated as quickly as possible after admission of the subject to the PHEC. For the purpose of this study, SOC is defined as efficient body cooling by physical methods and supportive measures, implemented as following:

Body Cooling

- *Ice packs*: should be placed to neck, axilla, and inguinal regions.
- **Evaporative cooling**: application of water (room temperature) over the body surface, via mist application with continuous use of a fan. Subjects may be covered with a thin sheet. Do not use ice/cold water immersion because of concerns with shivering (which could potentially worsen hyperthermia), and the need for IV access and other monitoring measures and medical procedures.
- **Benzodiazepines**: may be administered to ameliorate shivering induced by cooling methods, as deemed necessary by the Investigator.

Supportive Measures

Randomized subjects will also receive any other medical treatments and/or supportive measures (IV fluids, respiratory support) for the adequate treatment of existing complications or comorbidities (e.g. dehydration, seizures, aggressiveness, asthma) following acceptable medical practice, and as deemed necessary by the Investigator.

Treatment Groups

Upon admission to the PHEC, eligible patients with PDIT will be randomized in a ratio to one of the following treatment groups:

- Group A: Ryanodex[®], as added treatment to SOC
- Group B: SOC only

The Investigator will make all reasonable efforts to perform the **second** drug screen test during the screening process or as soon as feasible after randomization. The **second** drug screen test may not be feasible in some subjects, due to the dehydration, use of oxygen therapy and/or endotracheal intubation commonly seen in patients with PDIT, which may result in dryness of the oral mucosa. A blood sample for testing for the presence of psychostimulant drugs will also be collected after randomization.

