Subjects in Group A will receive SOC immediately followed by an initial dose of Ryanodex[®] (study drug) of 2.5 mg/kg administered as an IV bolus. Initial dose of Ryanodex[®] should be administered within minutes of randomization. The goal is to achieve an adequate clinical response, which is defined as meeting both of the following criteria:

2. Logistic Organ Dysfunction System (LODS) score ≤ 5

If the subject is not showing adequate clinical response between 10 and 30 minutes after the initial dose, or the subject had achieved an adequate response but afterwards signs/symptoms believed to be associated with PDIT re-appear a

second IV bolus dose of 2.5 mg/kg of Ryanodex[®] may be administered between 10 and 30 minutes following the initial dose. This repeat dosing is permitted, as deemed necessary by the Investigator, unless the subject demonstrates clinically significant signs/symptoms of dantrolene-related adverse reactions.

The Investigator must clearly record all clinical assessments and symptoms leading to repeat dosing of Ryanodex[®]. The total administered dose of Ryanodex[®] in a 24-hour period should not exceed 10 mg/kg.

Individual Subject Stopping Rules

- The Investigator may consider stopping study drug if the subject demonstrates clinically significant signs/symptoms of dantrolene toxicity, which may include, but are not limited to, the following: increased skeletal muscle weakness; worsening in the state of consciousness (e.g., lethargy, coma); worsening respiratory status, including increased respiratory muscle weakness, vomiting, diarrhea, or crystalluria; providing none of these signs/symptoms are not attributable to PDIT, a comorbid condition (e.g., asthma, epilepsy, pneumonia) or a concomitant medication (e.g., sedatives).
- The Investigator may stop study drug at any time for that subject's well-being if the Investigator believes that the subject has experienced a serious AE (SAE) possibly related to study drug or a clinically significant non-serious AE possibly related to study drug.
- The subject will be withdrawn from the study if a diagnosis had been made for which dantrolene is the SOC (e.g., malignant hyperthermia [MH]), and treatment with commercially available dantrolene should be initiated.

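### Does starting the TEAE window at the first randomised treatment leave the two groups with different time zeros?

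*SAP*

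**What the plan says.** The definition in SAP section 8.12.1 is: "Treatment Emergent AE's (TEAE) are defined as events with an onset on or after the first randomized treatment". TEAEs are then tabulated by treatment group. SAP section 8.8.4 counts SOC alone, or SOC with Ryanodex, as study treatment.

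The Protocol synopsis gives the order of events:

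- **Methodology.** After diagnosis, "the Investigator should initiate SOC treatment as quickly as possible, and will assess" eligibility.
- **Standard of Care.** SOC "should be initiated as quickly as possible after admission of the subject to the PHEC".
- **Treatment Groups, randomisation.** "Upon admission to the PHEC, eligible patients with PDIT will be randomized".
- **Treatment Groups, dosing.** "Subjects in Group A will receive SOC immediately followed by an initial dose" of Ryanodex, and that dose "should be administered within minutes of randomization". Any number of minutes is not visible in the text.
- **Main criteria for inclusion.** Women in Group A whose pregnancy result is pending may be randomised but wait for a negative result before Ryanodex.
- **Length of observation.** Subjects "are expected to remain at the study site for a maximum of 6 hours after screening". For those who move on to other care, "The Investigator will make all reasonable efforts to obtain" their medical data from the receiving facilities. Six hours is therefore a limit on the stay, not an adverse-event window.

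The synopsis rules out modelling or inference on safety and analyses the Safety population by actual treatment received. SAP sections 8.0 and 8.11 leave detailed methods and data conventions to a separate SAP, to be approved before the database is locked.

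**The concern.** In a trial where each arm starts a new drug after allocation, the first randomised treatment identifies itself. In this add-on design it does not. Group B receives nothing new after randomisation: its only treatment is SOC, which may already be running. Group A has SOC and then a drug dose. A programmer could open the window at SOC start, at randomisation or at first dose, and might choose differently in the two groups.

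Two things could then go wrong. A window that opens later in Group A collects fewer events there and makes Ryanodex look slightly safer with no true difference. A window that opens at SOC start in both groups is balanced, but may count events that came before randomisation. Safety and tolerability are the secondary objective, so a lopsided count would matter to readers of the tables. The primary endpoint is already timed from randomisation (SAP section 8.2.1.1) and is not at risk.

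**Working it through.** The plan states no figure to reproduce. The check has two parts: which readings the text supports, and how far each could move the tables.

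**Readings**

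1. *The assigned regimen, beginning with SOC.* SOC is the first component in both groups, so both windows open at SOC start.
2. *Only treatment given from randomisation onwards.* Group B opens at randomisation. Group A opens either at randomisation, because SOC is continuing there too, or at the first Ryanodex dose.
3. *Mixed.* Group B opens at SOC start and Group A at the first dose. This counts pre-randomisation SOC as randomised treatment in one group and not in the other, although both groups receive the same SOC. The text gives no ground for that.

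**Inputs, all assumed because the documents give none**

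- SOC lead before randomisation: L = 5 to 30 min.
- Delay from randomisation to Ryanodex: d = 2 to 10 min.
- Window from SOC start: W = 360 or 1,440 min. The time left after randomisation is T = W − L.
- Equal true risk in both groups and uniform onset over time.

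**Spurious SOC-to-Ryanodex ratio = Group B window ÷ Group A window**

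| Reading | Formula | Smallest | Largest |
|---|---|---|---|
| 1 | W/W | 1.00 | 1.00 |
| 2, both at randomisation | T/T | 1.00 | 1.00 |
| 2, Group A at first dose | T/(T − d) | 1435/1433 = 1.001 | 330/320 = 1.031 |
| 3, mixed | W/(T − d) | 1440/1433 = 1.005 | 360/320 = 1.125 |

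Under reading 1, the share of counted onsets that precede randomisation is L/W: from 5/1440 = 0.3% to 30/360 = 8.3%, the same in both groups.

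For women waiting on a pregnancy result, with d assumed to be 30 min, reading 2 with Group A opening at first dose gives 1435/1405 = 1.021 to 330/300 = 1.100. Their share of Group A is not given.

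**In subjects.** SAP section 8.12 summarises categorical safety data by frequency and percentage, so a count of subjects is the more relevant scale. Assume a 30% risk of at least one TEAE over 330 min and 50 subjects per group (the planned number). The risk over w minutes is 1 − 0.7^(w/330).

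- Reading 2, Group A at first dose, largest case: Group B 30.0%; Group A 1 − 0.7^(320/330) = 29.2%. The unrounded difference is 0.76 percentage points, and 50 × 0.0076 = 0.4 subject.
- Mixed reading, largest case: Group B 1 − 0.7^(360/330) = 32.2%; Group A 29.2%. The difference is 3.0 points, and 50 × 0.030 = 1.5 subjects.

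**The case for a change.** The strongest case for a change is that section 8.12.1 already states an operative definition, which a later SAP could copy unaltered. Timing both groups from randomisation would remove the doubt, match the primary endpoint, give a start time to a subject randomised to Group A but never dosed, and cost only wording and programming. Uniform onset may also be too kind in an acute illness. If risk is assumed to halve every 60 min, reading 2 with Group A opening at first dose gives [1 − 2^(−T/60)] ÷ [2^(−d/60) − 2^(−T/60)], which runs from 1.02 (L = 5, d = 2, W = 1,440) to 1.13 (L = 30, d = 10, W = 360).

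What stands is that the wording is ambiguous and that randomisation would be a sound anchor. The rest is weaker:

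- The 1.13 comes from the assumed decay together with the longest assumed delays. The documents support neither, and they point to short gaps: SOC and randomisation are both tied to admission, randomisation may go ahead before pending laboratory or pregnancy results, and the dose is due soon after it.
- Randomisation is not plainly better than first treatment. The Safety population is analysed by treatment received, and a randomisation anchor would call Group A events treatment-emergent before any Ryanodex had been given, so those events would need separate marking. Either anchor is defensible.
- The protocol's adverse-event section and the separate SAP are not among the supplied texts. A start-date convention there cannot be excluded, and that is where one would normally sit.

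**Conclusion.** The concern does not call for a change. The start event is under-specified, but no stated rule is shown to give a wrong result. Readings that treat SOC alike in both groups give a ratio of 1.00, or 1.00 to 1.03 under uniform risk if Group A opens at first dose. It is higher, up to 1.10, only in women kept waiting an assumed 30 minutes for a pregnancy result. On subject counts, the overall upper end is about 0.4 of a subject in 50 at an assumed 30% risk. The larger distortion, up to 1.125 or about 1.5 subjects, needs SOC to be classified differently in the two groups, and no careful analyst would do that. The remaining possibility, that some pre-randomisation events are counted, affects both groups equally.

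These sizes rest on assumed delays, windows and risk; the true size is unknown. What is affected is a descriptive table with no inference attached. The separate SAP, due before database lock, is the ordinary place for the analyst to settle the convention.

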#### 8.12.2 Clinical Laboratory Evaluations
